GEMS-T coaches will review participant logs prior to their scheduled one-on-one sessions. If there is missing data, the coach will obtain the information during the coaching session, including any information about adverse events (AEs). The GEMS-T Project Coordinator will review the exercise logs each Friday on non-coaching weeks for submission status and notification of AEs. For participants who have missing data, the GEMS-T Project Coordinator will attempt to contact them to remind them to complete the missing log entries and check to see if they are having any issues accessing the portal.

If a GEMS-S participant misses an exercise session, the facility coach will attempt to contact the participant to find out why and if the participant has had an AE. For follow up calls regarding missed exercise logs or sessions, the GEMS-T and GEMS-S Coaches will log the call date, result (reached/message left), and any important details in their log. If the coach cannot reach the participant, they should leave a voicemail reminding the participant to complete the log. If the participant has not updated their weekly log by the following Friday, the coach will attempt to contact them again.

- i. At the end of the 16 weeks of exercise, GEMS-S coaches will make a copy of the exercise logbook and upload it to a site-specific, secure Microsoft OneDrive folder housed by UAB. Research coordinators will request that GEMS-T participants bring in their exercise logbooks to their 16-week visit, whereupon they will make a copy of the logbook and upload to OneDrive. GEMS-T participants who forget to bring their logbook to the visit, will be given a stamped, addressed envelope to mail it to the site. The logbook will subsequently be returned by mail to the participant. See Data Safety and Adequacy section below for details on Microsoft HIPAA compliance.
- j. In order to respond to adverse events in a timely manner, the Project Coordinator at UAB will check exercise logs weekly and follow the adverse event reporting procedures outlined below.
- k. The project manager will follow up with the coaches for all the above items and take any necessary appropriate action.

[figure not shown]
COVID-19 Intervention Procedures

While site training facilities are closed, we will implement the following procedures for GEMS-S participants in weeks 1 to 16 of exercise:

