Although evidence suggests that exercise can improve mobility and perhaps decrease the rate and extent of disability (i.e. impaired function) in people with MS, most studies related to exercise have failed to screen for people with walking problems using objective assessment.²¹⁻³⁸ Evidence does show, however, that traditional, facility-based exercise training, particularly in a setting where other people with MS are exercising or under the supervision of exercise personnel, may help people with MS consistently participate in exercise or to exercise at a higher, more intense level. Despite this evidence, lack of access to these programs may make it difficult to engage in a GEMS-S program.³⁹⁻⁴³ Telerehabilitation (telerehab) has great potential to overcome challenges associated with facility-based programs. Telerehab can include videoconferencing, remote monitoring of signs and activity, and dissemination of specialized and individualized information via electronic mechanisms. Both facility-based and telerehab exercise training have yielded positive results in people with MS,²¹⁻³⁸ but have not been compared head-to-head. The current study will fill this gap in the evidence base and compare the outcomes of delivering the same exercise interventions in a facility (facility-based exercise training or GEMS-S) or in the home/community using a telerehab approach (telerehab delivered exercise training or GEMS-T). The interventions are designed to be identical in content, with the only difference being the mode of training delivery.

This study will yield important data to inform people with MS who have objective walking impairment, as well as healthcare providers, exercise trainers, payers, and policy makers, about exercise options for people with MS. Our **main hypothesis** is that there will be no difference in outcomes when the evidence-based individualized exercise program is delivered in a facility (GEMS-S) or via telerehab (GEMS-T) (i.e., walking and other outcomes will improve similarly between conditions). Our null hypothesis is that GEMS-T is inferior to GEMS-S. A secondary hypothesis is that patients who perform their preferred **choice** of program (GEMS-T(Choice) or GEMS-S(Choice)) will have better outcomes in self-efficacy, adherence, and adoption of exercise than no choice conditions.

SPECIFIC AIMS

Our specific aims (SAs) are as follows:

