- SA1: Compare the extent of change pre-test to post-test in walking and mobility outcomes, social and vocational participation, and quality of life between the identical evidence-based individualized exercise program delivered via GEMS-S or GEMS-T in adults with MS who have slowed walking (greater than 6 seconds on the T25FWT);
- SA2: Evaluate and compare the effectiveness between participants randomized to their preferred delivery mode (GEMS-T(Choice) or GEMS-S(Choice)) and those who are not randomized to their preferred delivery mode (GEMS-T or GEMS-S);
- SA3: Evaluate changes in self-efficacy, and adoption of exercise between these groups (GEMS-T, GEMS-S, GEMS-T(Choice), GEMS-S(Choice)).

RESEARCH METHODS

Design

This is a multi-site, 2-staged randomized, choice design study aimed at noninferiority, to compare the effectiveness of delivering an individualized exercise program in a facility (facility-based exercise training or GEMS-S) versus via telerehabilitation (telerehab-based exercise training or GEMS-T) in people with MS. Noninferiority assumes both interventions (GEMS-S and GEMS-T) produce no statistically different outcomes.

Shepherd Center is the Clinical Coordinating site, led by [name], and UAB is the Training Site, led by [name]. UAB will also house the Statistical Center, led by [name]. The Data Management Center led by [name] will be maintained by iConquerMS of the Accelerated Cure Project.

This protocol will first outline site specific procedures and tools, and then will provide details regarding the coordination of the multiple study sites by the investigators at the Shepherd Center.

Participants

We will enroll 400 participants across the following eight centers: The Shepherd Center, Atlanta, GA; the University of Georgia, Athens; the Cleveland Clinic Mellen Center for MS Treatment and Research, Ohio; the University of North Carolina, Chapel Hill; Massachusetts General Hospital, Boston (MGH); the University of Colorado; the University of Alabama, Birmingham (UAB) in collaboration with The Tanner Center and Foundation for Neurological Diseases (Tanner Center); and Marquette University, Wisconsin. The criteria for eligibility will be identical at all sites. Participants will qualify for the study if they meet the following criteria:

Inclusion criteria:

1. Physician-confirmed diagnosis of MS
2. Expanded Disability Status Scale (EDSS) score of 4.0 through 6.5
3. Age between 18 and 65 years

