If a physician instructs a participant to pause exercising, the site research coordinator must obtain medical clearance from the participant's physician before resuming exercise. If the participant's physician does not instruct a participant to stop exercising, the site PI determines whether or not medical clearance after an AE is required.

Site research coordinators will inform the participant's coaches when medical consent has been obtained and the participant is approved to resume exercising.

Figure 3 below provides additional detail regarding how AEs are reported and addressed.

[figure not shown]
[figure not shown]

Figure 3: AE Reporting and Follow up Procedures

DATA ANALYSIS

Data analysis plan

The primary hypothesis is a non-inferiority test of the changes in T25FWT between GEMS-T and GEMS-S. This will be tested using a linear model with site as the stratification factor and an intention to treat approach. The primary analysis will adjust for covariates age, gender and baseline EDSS or PDDS. Further addition of covariates may be examined in sensitivity analyses based on any differences seen on examination of baseline variables between groups. Secondary endpoints include change in 6MWT and EDSS/PDDS. In all endpoints, we are assessing

improvement over baseline values. We will examine the frequency of worsening as a safety comparison. We will also examine the primary endpoint of a 20% improvement in the T25FWT (yes or no) using logistic regression. Further, to characterize the changes over time, we will use linear mixed models to assess the slopes of change for GEMS-S versus GEMS-T groups. We will also examine the relationship between the dose of exercise measured by compliance and the change in the primary and secondary outcomes. These are exploratory outcomes to see if the compliance measures predict the benefits on the outcomes. This information is important for translation and information dissemination to people with MS.

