Protocol Title: Comparative Effectiveness of an Exercise Intervention Delivered via Telerehabilitation and Conventional Mode of Delivery

Statistical Analysis Plan

PI: [name], Ph.D.

Version: 6/17/2022

Sponsor: Patient Centered Outcomes Research Institute (PCORI)

NCT Number: NCT03468868

Data analysis plan

SA1: Compare the extent of change in walking and mobility outcomes, social and vocational participation, and quality of life. The primary hypothesis is a non-inferiority test of the changes in T25FWT between TET and FET. This will be tested using a linear model with site as the stratification factor included using an intention to treat approach (imputation for missing values are discussed below). The primary analysis will adjust for covariates age, gender and baseline EDSS. Further addition of covariates may be examined in sensitivity analyses based on any differences seen on examination of baseline variables between groups. Secondary endpoints include change in 6MWT and EDSS. In all of these endpoints we are looking at improvement over baseline values whereas many MS studies focus on worsening. We will examine the frequency of worsening as a safety comparison. We will also examine the primary endpoint of a 20% improvement in the T25FWT (yes or no) using logistic regression. Further, to characterize the changes over time, we will use linear mixed models to assess the slopes of change for FET versus TET groups. We also will examine the relationship between the dose of exercise measured by compliance and the change in the primary and secondary outcomes. These are exploratory outcomes and will be assessed with no corrections for multiple testing and are important mostly for descriptive analyses to see if the compliance measures indeed predict the benefits on the outcomes as this information is important for translation and information to people with MS.

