Data linkage plan. Each participant will be assigned a study ID number when randomized to the intervention group by the biostatistician. This will be the only identifier in all databases and systems used in this study. The Shepherd Center will maintain the master file. None of the investigators or staff involved in the assessments will have access to the identifier data, and thus will remain blinded to the assignment for the entire intervention phase.

Sensitivity analyses. Randomization should balance covariates across treatment groups, but this will be checked with frequency and means tables, and chi-square/Fisher exact and F-tests/t-tests respectively. If treatment groups show important imbalances among covariates, then they can be adjusted for using covariates in various types of regression models as we noted above under the primary analyses. As noted briefly in the primary analysis section, per protocol analyses will be used to support the conclusions of the intention to treat analyses. In the intention to treat analyses we must take into account dropouts. For anyone with at least one post randomization timed walk test, we will impute a model based final endpoint to assess change. Key sensitivity analyses will include adjustment for covariates: age, gender, sex and treatment preference at entry. Interaction terms will be used to identify potential impacts of key covariates. In addition, imputation for missing values will be conducted to assess the impact of these lost observations. We note again that rules are in place to deal with the time variables. For other variables (MSWS, MFIS and NeuroQOL, EDSS) will require various forms of imputation for sensitivity analyses. We will use a general approach discussed below for imputation of these secondary endpoints and use per protocol versus ITT for sensitivity analysis. For the major analyses, best case and worst case analyses will be done. Subgroup analyses will attempt to quantify the consistency of the findings amongst subgroups.

Management of missing data

a. Methods to prevent and monitor missing data.

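### The Protocol's only definition of non-inferiority is the absence of a statistical difference, which conflicts with its own null, and the documents supplied give no margin, alpha or confidence-limit rule for the primary T25FWT test

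*Protocol*

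**What the plan says.** The Protocol (Research Methods, Design) says: "Noninferiority assumes both interventions (GEMS-S and GEMS-T) produce no statistically different outcomes". This is the only definition of non-inferiority in either document.

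The Protocol's background section gives two further statements. The main hypothesis is worded as follows: "there will be no difference in outcomes when the evidence-based individualized exercise program is delivered in a facility (GEMS-S) or via telerehab (GEMS-T"), and the same sentence explains this as similar improvement in walking and other outcomes. The null follows: "Our null hypothesis is that GEMS-T is inferior to GEMS-S".

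The analysis text names the test. The Protocol's Data analysis plan says "The primary hypothesis is a non-inferiority test of the changes in T25FWT between GEMS-T and GEMS-S", and SAP SA1 says "The primary hypothesis is a non-inferiority test of the changes in T25FWT between TET and FET". Both specify a linear model with site as stratification factor, intention to treat, and adjustment for age, gender and baseline disability. The SAP's Sensitivity analyses add that "per protocol analyses will be used to support the conclusions of the intention to treat analyses". SAP heterogeneity section, part a, allows for the possibility that non-inferiority is not demonstrated.

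No margin, alpha, sidedness or confidence-limit rule for this test appears in the documents supplied.

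**The concern.** A non-inferiority test starts from the null that the new mode is worse by at least some amount, and rejects it when the confidence interval excludes a deficit of that size. A non-significant difference excludes nothing. It can arise because the modes are alike, or because the data are too few or too noisy to separate them. The Design sentence and the stated null therefore lead to different decisions from the same data.

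With no numerical rule stated, the Design sentence is the only criterion a reader can apply. Under it, GEMS-T could be reported as non-inferior while the interval reaches well into GEMS-T being worse, and losing data makes that conclusion easier to reach. Data loss is a live issue here: the Protocol's COVID-19 follow-up procedures suspend the T25FWT while sites are restricted.

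**Working it through.** **Does any text supply the rule?** Four candidates were checked.
- The 20% T25FWT improvement (Protocol Data analysis plan; SAP SA1) is a within-participant yes/no outcome for logistic regression, not a between-arm margin.
- The 95% confidence intervals in SAP heterogeneity section, part c, are for subgroup estimates.
- The per protocol analysis adds an analysis set, not a criterion.
- The remark in part a about not demonstrating non-inferiority does not say what would demonstrate it.

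**The plan's own figure.** The only sizing figure is N = 400, with 200 Choice and 200 No Choice, the latter randomized 100:100 (Protocol, Participants). It cannot be reproduced, because no margin, SD, alpha or power is given. The dependence on the margin is strong. At one-sided 0.025, 80% power and no true difference, the required n per arm is 393, 175, 99 and 63 for margins of 0.2, 0.3, 0.4 and 0.5 SD.

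**How the two criteria differ (illustration).** Everything is in SD units of T25FWT change. SD, margin and two-sided 5% are assumed. The base case is unadjusted, without dropout, and with an even split among choosers for 200 per arm.

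SE = √(1/n₁ + 1/n₂), multiplied by √0.7 if covariates explain 30% of variance.

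P(non-significant | true deficit d) = Φ(1.96 − d/SE) − Φ(−1.96 − d/SE).

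At 100:100, SE = √(2/100) = 0.1414 and 0.3/0.1414 = 2.121, so P = Φ(−0.161) = 0.436 (the second term is negligible). At 200:200, SE = 0.1000 and P = Φ(1.96 − 3.00) = Φ(−1.04) = 0.149.

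| Case | n | SE | P(non-significant), d = 0.3 |
|---|---|---|---|
| Base | 100:100 | 0.1414 | 0.436 |
| Base | 200:200 | 0.1000 | 0.149 |
| Choosers split 70:30 | 240:160 | 0.1021 | 0.164 |
| Choosers split 80:20 | 260:140 | 0.1048 | 0.184 |
| 20% dropout | 80:80 | 0.1581 | 0.525 |
| 20% dropout | 160:160 | 0.1118 | 0.235 |
| Covariates explain 30% | 100:100 | 0.1183 | 0.282 |
| Covariates explain 30% | 200:200 | 0.0837 | 0.052 |

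A confidence-limit test with M = 0.3 SD passes at a true deficit of 0.3 SD with probability Φ(−1.96) = 0.025 in every row. At a true deficit of 0.4 SD, the base-case non-significance rates fall to 0.193 and 0.021.

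**Where the difference ends.** A result is non-significant with GEMS-T observed up to 1.96 × SE worse: 0.277 SD at 100 per arm and 0.196 SD at 200. The upper 95% limit is then 3.92 × SE: 0.554 and 0.392 SD. If M is at least that large, every non-significant base-case result also passes the confidence-limit rule.

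**The case against.** The strongest case on the other side is that the analysis text points away from the Design sentence. The null is directional, the primary test is called a non-inferiority test in both documents, and the SAP treats non-inferiority as something to be demonstrated. The Design sentence is explanatory and does not purport to be a decision rule. This stands in part: declaring non-inferiority from a non-significant result is a risk the wording allows, not a stated plan. But none of this text says what would demonstrate non-inferiority.

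Three stronger readings are tempting, and the documents do not support them.
- *The main hypothesis also contradicts the null.* It need not. Expecting no true difference while testing a null of inferiority is the usual arrangement, and the same sentence speaks of similar improvement. The firm conflict is between the Design sentence and the null.
- *The trial has no margin.* The SAP refers to material that is not in it, such as rules for the time variables and a Table 5. A margin may be set elsewhere. What can be said is that it is not stated in the documents supplied.
- *The primary contrast is certainly the randomized No Choice cells.* SA3 lists "adoption of exercise between these groups (GEMS-T, GEMS-S, GEMS-T(Choice), GEMS-S(Choice"), so the unsuffixed labels there mean No Choice, and SA2 uses them in the same way. But the Intervention section gives n = 200 per mode. The SA2 analysis also reuses the primary model with a choice-by-treatment interaction. These suggest all participants by mode, without settling it.

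It is also fair that the 44% figure needs the smaller set and a true deficit equal to the assumed margin.

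**Conclusion.** The concern holds: the Design sentence is wrong as written, and the documents supplied contain no rule that corrects it. This must be fixed before the primary comparison is made, because without a margin and a confidence limit the named test cannot be carried out from these documents.

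The size is conditional on assumptions that the documents do not supply. At a true deficit of 0.3 SD, the non-significance criterion accepts GEMS-T in 44% of trials at 100 per arm and 15% at 200. If covariates explain 30% of variance, the rates are 28% and 5%; with 20% dropout they are 53% and 23%. The matching confidence-limit test accepts it in 2.5%. The risk is small for large deficits in the pooled set (2% at 0.4 SD). It vanishes in the base case for margins of at least 0.55 SD (100 per arm) or 0.39 SD (200 per arm).

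Confidence is high that the rule is not stated here. Whether it exists elsewhere is unknown.

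Two related points are left open. Both documents also attach the label of primary endpoint to the 20% responder outcome, so it is unclear which T25FWT endpoint carries the claim. The comparison set is ambiguous too; this is secondary, but it decides whether the primary contrast is fully randomized.

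**What to change.** 1. Replace the Design sentence with: *Non-inferiority means that GEMS-T is not worse than GEMS-S by more than margin M.* Align the main hypothesis with it.
2. Add to the Protocol's Data analysis plan and to SAP SA1: *GEMS-T is declared non-inferior only if the upper confidence limit for the adjusted GEMS-T minus GEMS-S difference in T25FWT change (follow-up minus baseline, larger is worse) is below M. A non-significant difference is not evidence of non-inferiority.* Reverse the sign if change is scored as improvement.
3. State M with units and justification, the alpha and sidedness, and the time point. SA1's wording, "Compare the extent of change pre-test to post-test in walking and mobility outcomes", suggests the 16-week visit; the sponsor should confirm. Fix these before any unblinded comparison or, if they are already set in another study document, insert them with source and date.
4. State that continuous T25FWT change carries the non-inferiority claim, and relabel the 20% responder outcome accordingly.
5. State whether the primary contrast uses the 100:100 randomized No Choice cells or all participants by mode, and use one set of labels for it in both documents.

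The cost is wording plus a margin justification. The effect on the chance of success depends on M. With M = 0.3 SD and no true difference, power is Φ(0.3/SE − 1.96): 56% at 100 per arm and 85% at 200, against a 95% chance of non-significance. The order reverses once M exceeds (1.96 + 1.645) × SE, which is 0.51 SD at 100 per arm and 0.36 SD at 200; the confidence-limit rule is then the easier one to pass.

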4. Able to travel to a GEMS-S site for testing and training
5. Accessible, technological platform for GEMS-T (i.e. computer or DVD player and TV,

and telephone)

6. A score of between 25 and 75 on the MSWS-12
7. Timed 25-foot walk test (T25FWT) time of between 6 seconds and 3 minutes
8. Medically stable or approval from physician to participate in exercise studies
9. A score of between 3 and 6 (inclusive) on the Patient Determined Disability Steps

Exclusion criteria:

1. Documented MS relapse in the past 30 days
2. Have had falls in the past three months that the study investigator determines makes participation unsafe
3. Unable to walk 25 feet
4. Already exercises at recommended levels as determined by a score of 25 or higher on the Godin Leisure-Time Exercise questionnaire
5. Has other neurological (e.g., stroke) or musculoskeletal conditions or other co-morbidities
6. Has cognitive difficulties as determined by a Mini Mental Status Exam score <19
7. Is not proficient in English
8. Is physically unable to complete the second T25FWT trial
9. Any other concern that the investigators deem would jeopardize the safety of the potential participant.

We will randomize 200 participants to the Choice group and 200 to the No Choice group. Those in the Choice group will choose which exercise program to undertake – GEMS-T or GEMS-S. In the No Choice group, we will randomize 100 participants to GEMS-S and 100 to GEMS-T (see Figure 1). Four sites (Shepherd Center with help from UGA, Marquette University, Cleveland Clinic, and University of Colorado) will each recruit 80 participants. UNC and MGH will together recruit a total of 40 participants. UAB will recruit at least 40 participants with help from the Tanner Center, a Birmingham-based multidisciplinary center providing neurology, nursing, infusion, clinical research, neurodiagnostic testing, occupational therapy, physical therapy, speech/language pathology, licensed professional counseling, group wellness classes, and individual personal training in one central location.

[figure not shown]

Figure 1: Randomization Scheme for Each Participant

Recruitment methods

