Patient Determined Disability Steps	Participant chooses one of 9 categories that describes their MS disability level.		X			X		X	X
MS Walking Scale-12	A 12-item self-report survey; measures the impact of MS on walking ability and daily activities over the past 2 weeks.		X	X	X	X	X	X	X
Godin Leisure-Time Exercise Questionnaire	4 questions; 7-day recall of leisure-time physical activity to determine if individual is already exercising at adequate levels.		X			X	X	X	X
Exercise Preparticipation Health Screening	Questionnaire about physical health to determine if medical consent to participate is required.		X						
Expanded Disability Status Scale	A 30-minute multiple item disease-specific instrument that characterizes disability level and determines disability progression in people with MS.			X			X		X
Timed 25 Foot Walk Test	Measure of walking speed; participant will perform twice. Only one trial must be in the eligibility range for inclusion (6 to 180 seconds). The time of both trials will be averaged for the outcome measure. Participants will be ineligible if physically unable to complete trial 2. If the assistive device/orthosis changes from pre- to post training, participants will be tested with the previous device.			X			X		X
6-Minute Walk Test	Measures the distance an individual can walk over a total of six minutes on a hard, flat surface. The goal is for the individual to walk as far as possible in six minutes. The individual can self-pace and rest as needed as they traverse back and forth along a marked walkway. If the assistive device/orthosis changes from pre- to post training, participants can choose device type, or no device at all.			X			X		X
Mini-Mental Status Exam	11-item test of cognitive impairment.			X					
Demographic survey/medication	Age; gender; type and history of MS; race/ethnicity; insurance status; living arrangements.				X	X	X	X	X
Short Assessment of Health Literacy-English (SAHL-E)	SAHL-E contains 18 items to assess an English-speaking adult's ability to read and understand common medical terms and estimate an adult's health literacy level.				X				
Neuro-QOL	A validated outcome measure of quality of life sponsored by the National Institute of Health recommended by the American Academy of Neurology.				X	X	X	X	X
Modified Fatigue Impact Scale-21	A 21-item self-report of the severity of fatigue and its effect on the participant's activities and lifestyle over the past 4 weeks.				X	X	X	X	X

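### The scale of the primary T25FWT change is not stated and baseline T25FWT is not a covariate; if change is in seconds, slow walkers carry disproportionate weight relative to the plan's own 20% benchmark

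*Protocol*

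**What the plan says.** - **Range.** Protocol, Participants, inclusion criterion 7: "Timed 25-foot walk test (T25FWT) time of between 6 seconds and 3 minutes". Protocol Table 1 applies the limits loosely: "Only one trial must be in the eligibility range for inclusion (6 to 180 seconds"), so the averaged baseline can fall outside them.
- **Measurement.** Protocol Table 1: "The time of both trials will be averaged for the outcome measure".
- **Primary test.** Protocol, Data analysis plan: "The primary hypothesis is a non-inferiority test of the changes in T25FWT between GEMS-T and GEMS-S". SAP, SA1, says the same with its own arm labels (TET for GEMS-T, FET for GEMS-S): "The primary hypothesis is a non-inferiority test of the changes in T25FWT between TET and FET".
- **Model.** Protocol: "This will be tested using a linear model with site as the stratification factor and an intention to treat approach". SAP: "The primary analysis will adjust for covariates age, gender and baseline EDSS"; the protocol allows PDDS in place of EDSS. Baseline T25FWT is not listed in either document.
- **Benchmark.** SAP, SA1, also has a logistic regression of "the primary endpoint of a 20% improvement in the T25FWT", a relative criterion.
- **Not stated.** Neither document gives a log, speed, percent, rank or robust analysis of the continuous endpoint, a non-inferiority margin, an SD, an alpha level or an expected baseline distribution. SAP, Sensitivity analyses, mentions rules for the time variables but does not set them out.

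**The concern.** Averaged times, a change and a linear model together suggest a difference in seconds. That model gives every second equal weight and assumes a common residual variance. If walking times vary in proportion to their level, slow walkers contribute most of the noise and have most of the leverage. The 20% criterion, by contrast, treats a given relative change as the same benefit at any walking speed. The two analyses that the plan calls primary would then weigh the same patient's change differently.

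Omitting baseline T25FWT adds to this. Under proportional response, change in seconds depends on where the patient started. Age, gender and EDSS capture only part of that, so a chance imbalance in baseline times would stay in the mode comparison.

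At stake are precision and a clear meaning for the margin. A margin in seconds and a margin as a ratio are different standards, and a non-inferiority margin cannot be fixed until the scale is.

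**Working it through.** **1. The plan's own figure.** The total of 400 cannot be reproduced, because margin, SD, alpha, power and dropout are all absent. Inverting the usual formula, margin/SD = (z(1-alpha) + z(power)) x sqrt(2/n), shows what the arms could support at one-sided 0.025 (assumed) with no true difference:
- 200 per mode: (1.960 + 0.842) x sqrt(2/200) = 0.28 at 80% power; 0.32 at 90%.
- 100 per mode (No Choice group only): 0.40 at 80% power; 0.46 at 90%.

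This says nothing about seconds or percent until an SD on a named scale is supplied.

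**2. Scale arithmetic (document figures).**
- 20% of 6 s = 1.2 s; 20% of 180 s = 36 s; 36/1.2 = 30.
- One 180 s walker changing by 20% shifts an arm mean by 36/100 = 0.36 s or 36/200 = 0.18 s.
- One 10 s walker changing by 20% shifts it by 2/100 = 0.02 s or 2/200 = 0.01 s.

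**3. Variance share and effective sample size (all inputs assumed).** Baselines are lognormal with median 8-10 s before truncation to 6-180 s. Retest error is proportional, with log SD 0.15 or 0.25, and there are 400,000 draws per scenario. The 20% margin is borrowed from the responder criterion for illustration; it is not a proposed margin. The effective-n ratio of log to raw analysis is

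(ln 1.2 / SD of log change)^2 / (0.2 x mean baseline / SD of raw change)^2.

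| Log SD of baseline | Mean baseline (s) | 95th percentile (s) | Variance share, slowest 10% | Effective-n ratio |
|---|---|---|---|---|
| 0.3 | 9.0-10.7 | 13.5-16.4 | about 0.24 | 0.91-0.99 |
| 0.4 | 9.8-11.5 | 16.3-19.7 | about 0.29 | 0.96-1.04 |
| 0.5 | 10.9-12.5 | 19.7-23.8 | 0.34-0.36 | 1.01-1.11 |
| 0.75 | 14.2-16.2 | 31.9-37.9 | 0.51-0.53 | 1.26-1.40 |
| 1.0 | 19.0-21.5 | 51.4-60.0 | about 0.64 | 1.56-1.72 |

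On the log scale the slowest 10% supply 10% of the variance under this error model. The ratio can fall below 1 because ln 1.2 = 0.182 is a tighter margin than 0.2: (0.182/0.2)^2 = 0.83. Skew has to overcome that factor before the log scale gains.

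**4. A second set of assumptions.** Here log change has mean -0.1 and SD 0.2, with 200 per arm, one-sided 0.025, and a margin of 5% of the median baseline (ln 1.05 on the log scale). As the 95th percentile of baseline rises through 13, 22, 35 and 50 s:
- the slowest 5% carry 14%, 24%, 37% and 47% of the variance of raw change, against 5% on the log scale;
- power on seconds is 0.69, 0.57, 0.41 and 0.30, against 0.68 on the log scale.

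**5. The contrary case.** If retest error is constant in seconds, the variance of change does not depend on baseline and the log analysis gains no precision.

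**The case against.** **The scale is inferred.** This stands. Averaging two trials defines the measurement, not the scale of change, and a linear model fits log or percent change equally well. The unpublished time-variable rules might settle it. But an unnamed primary scale in a non-inferiority trial is itself the gap, and the remedy is the same.

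**A few slow walkers decide the result.** A reader might infer this from the 30-fold range. The documents do not support it. Without a margin, an SD or a baseline distribution, no change of verdict can be demonstrated. A large share of variance is a loss of precision, not bias, since slow walkers in the No Choice group are randomized between modes. Very slow walkers may also be few. The limits on EDSS (4.0-6.5), MSWS-12 (25-75) and PDDS (3-6) narrow the case mix. In the simulations, baselines above 120 s make up under 0.7% in every scenario, fewer than 0.007 x 400 = 2.8 participants.

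**The gain depends on assumed skew.** This stands too. At log SD 0.3 to 0.4 the two scales are about equal, with log slightly worse in most of those scenarios.

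**The 20% responder analysis already works on a relative scale.** Partly. A responder threshold does not commit the plan to a proportional continuous effect, and having both analyses is not a contradiction. But the responder analysis dichotomises, carries no non-inferiority margin and has no stated rank against the continuous test.

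**Log is one option among several.** Agreed. Speed, percent change, ranks or a robust variance are also defensible, so log need not be the sole primary scale.

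**Conclusion.** The point holds in limited form. From the documents alone: the scale of the primary change is unstated, baseline T25FWT is not in the model although it is collected, eligible times span 6 to 180 s, and the only benchmark is relative. If the analysis is in seconds, equal relative changes are weighted up to 30 to 1.

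The cost in precision runs from none, under mild skew or constant-seconds error, to the equivalent of about 1.7 times the sample size under strong skew with proportional error. That range rests on assumed baseline and error distributions. It is not evidence that the non-inferiority conclusion would change. The case for acting is that the protection is nearly free and that scale and margin have to be settled together anyway.

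**What to change.** In SAP, SA1:
1. Name the scale of the primary T25FWT change, the time point (16 weeks) and the margin on that scale.
2. Add baseline T25FWT, the average of the two trials, to site, age, gender and baseline EDSS in the primary model. This removes baseline-related differences; it does not equalise variance, so item 3 is still needed.
3. Pre-specify log T25FWT at 16 weeks adjusted for log baseline, with the same other covariates, as the key supporting analysis, or as primary if the sponsor prefers. Report the mode effect as a ratio of GEMS-T to GEMS-S with its confidence interval against a ratio margin, and give the difference in seconds alongside. State in advance which analysis decides non-inferiority.
4. Write out the time-variable rules to which the SAP refers.

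Cost: SAP wording and one extra analysis, with no new data. The drawback is that the log-scale effect is a percentage difference rather than seconds, which is why both should be shown.
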